		Clinical Study Protocol		
Modified:	24Jun2024		Author:	[name]
Version:	1.0		Approvers:	[name]/[name]
Status:	Final		Page:	7 of 29

The Amara View mask, although already cleared for marketing by the US FDA, is undergoing considerations for design changes. A new competitor minimal contact full-face mask (ResMed AirFit F40) has been recently cleared for marketing by the US FDA and released to the market. Prior to making design updates, this study will evaluate patient preference of the Amara View mask compared to the AirFit F40 to provide feedback to the design team.

Description of the Intervention Studied

Investigational Products

There are no investigational products in this benchmark clinical study.

Products Cleared for Marketing by the US FDA

- Amara View Minimal Contact Full Face Mask (MCFFM)

The Amara View Full-Face Mask is a minimal contact full face mask manufactured by Philips Respironics (Murrysville, PA) that covers the mouth and seals under the nose compared to traditional full-face masks which seal over the nose. The Amara View mask is intended to reduce discomfort on the bridge of the nose. There is no forehead arm, offering patients an enhanced design to keep the field of vision clear. The mask consists of a cushion assembly with three cushion sizes, and a modular frame assembly connected to an entrainment elbow and headgear with two size options. The silicone cushion seals under the nose and around the outer perimeter of the patient's mouth and contains a cutout that allows the nostrils to inhale and exhale through when the mask is under pressure. The cushion assembly can be removed from the frame assembly for cleaning or for replacement of the cushion assembly. This allows for one frame size to attach to all three cushion sizes. A quick release tube with a built-in swivel provides a means for connecting the mask to the breathing circuit. The mask can be secured to the patient via headgear, which attaches to the frame with either magnetic clips or non-magnetic talon clips. Amara View uses a traditional tube in front of the mask with a pig tail tube.

The Amara View MCFFM is for single-patient use in the home or multi-patient use in the hospital/institutional environment. The mask is intended to be used on patients (>66lbs/30kg) for whom CPAP or bi-level therapy has been prescribed.

- AirFit F40 Minimal Contact Full Face Mask

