The AirFit F40 is a minimal contact FFM manufactured by ResMed (San Diego, CA) that rests softly and securely under the patients nose and is designed to let patients sleep in any position and move freely throughout the night. The mask consists of three cushion sizes and three headgear sizes. Headgear adjustments can be made with magnetic clips that easily snap on and off.

The AirFit F40 MCFFM is for single-patient reuse in the home environment. The mask is intended to be used on patients weighing more than 66lbs (30kg), who have been prescribed non-invasive CPAP or Bi-level positive airway pressure therapy.

Study Objectives

The primary objective of the study is to assess patient preference for the Philips Respironics Amara View MCFFM compared to the competitor ResMed AirFit F40 MCFFM. The secondary

Document ID:	N/A	Document title:	Classification:	For internal use
		Clinical Study Protocol		
Modified:	24Jun2024		Author:	[name]
Version:	1.0		Approvers:	[name]/[name]
Status:	Final		Page:	8 of 29

aim of the study is to compare PAP therapy device data between the two masks. A detailed description of the aims is presented in the following table.

Objectives	Hypothesis	Endpoints
To determine patient preference for the Amara View compared to the AirFit F40 as determined by ratings of mask attributes.	Subjective ratings on mask attributes will tend to be higher for the Amara View mask compared to the ratings for the AirFit F40 mask.	
Comparison in satisfaction ratings between the Amara View and the AirFit F40 will be measured for the following attributes:
 
 • Bed partner satisfaction (overall) • Fit (cushion, headgear, frame, mask overall) • Comfort (cushion, headgear, frame, mask overall) • Ability to maintain a seal during use (seal satisfaction, leak location) • Stability of the mask • Noise level (self, bed partner) • Air venting (self, bed partner) • Comfort of breathing • Sleep quality • Visual appeal • Patient Satisfaction overall (headgear, cushion, frame, mask) 
Difference in NPS between the Amara View and the AirFit F40
 
Differences in ease of use and satisfaction ratings between the Amara View and the AirFit F40
 
 • Mask clips • Mask overall • Assembly (elbow, cushion, frame, tubing quick disconnect, mask clips) • Disassembly (elbow, cushion, frame, tubing quick disconnect, mask clips)

Document ID:	N/A	Document title:	Classification:	For internal use

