- Any unstable medical condition (e.g., uncontrolled cardiac, lung, or neurological disease) or limitation that would affect the participant's ability to complete trial activities
- Experiencing any acute illness (e.g., acute sinusitis, ear or eye infections, upper respiratory infections, pharyngitis, bronchitis, pleurisy, pneumonia, or facial dermatitis) that would impact their ability to use the mask and/or PAP therapy during the trial
- Surgical procedures involving the head, neck, face (eyes, ears, nose), or lungs in the previous 90 days or taking place any time during the trial period
- Pregnant
- Advised by a health care provider to avoid magnets
- Patient or patient's household member, caregiver or bed partner in close vicinity currently using medical implants or medical devices that would be affected by magnets, including but not limited to:
 - Pacemakers
 - Implantable cardioverter defibrillators (ICD)
 - Neurostimulators
 - Magnetic metallic implants/electrodes/valves placed in upper limbs, torso, or higher (i.e., neck and head)
 - Cerebral spinal fluid (CSF) shunts (e.g., ventriculo peritoneal (VP) shunt)
 - Aneurysm clips
 - Embolic coils
 - Intracranial aneurysm intravascular flow disruption devices
 - Metallic cranial plates, screws, burr hole covers, and bone substitute devices
 - Metallic splinters in the eye
 - Ocular implants (e.g., glaucoma implants, retinal implants)
 - Certain contact lenses with metal

Document ID:	N/A	Document title:	Classification:	For internal use
		Clinical Study Protocol		
Modified:	24Jun2024		Author:	[name]
Version:	1.0		Approvers:	[name]/[name]
Status:	Final		Page:	16 of 29

- Implants to restore hearing or balance that have an implanted magnet (such as cochlear implants, implanted bone conduction hearing devices, and auditory brainstem implants)
- Magnetic denture attachments
- Metallic gastrointestinal clips
- Metallic stents (e.g., aneurysm, coronary, tracheobronchial, biliary)
- Implantable ports and pumps (e.g., insulin/infusion pumps)
- Hypoglossal nerve stimulators
- Devices labeled as MR (Magnetic Resonance) unsafe
- Magnetic metallic implants not labeled for MR or not evaluated for safety in a magnetic field
- PAP device is unknown, or they are using a recalled device that has not yet been remediated. Recalled devices include:
 - DreamStation CPAP, Auto CPAP, or BiPAP
 - DreamStation BiPAP, autoSV (ASV)
 - DreamStation ST, AVAPS (Also known as DreamStation BiPAP AVAPS or DreamStation BiPAP S/T)

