 - DreamStation Go CPAP, APAP or Auto CPAP
 - Dorma 400 or 500 CPAP or Auto CPAP
 - System One ASV4
 - System One (Q-Series) 50 series CPAP, Auto CPAP, or BiPAP
 - System One (Q-Series) 60 series CPAP, Auto CPAP, or BiPAP
 - C Series ASV, S/T, or AVAPS
 - REMStar SE Auto CPAP

Withdrawal

The term 'discontinuation' refers to the participant's premature withdrawal from the study prior to completing all procedures. Participants may be discontinued from the study for any of the following reasons:

- At the discretion of the PI or his designee, if he believes that continuing with the protocol is not in the best interest or may prove harmful to the participant. Such a decision may be precipitated by adverse events, including fever, nausea, rash, changes in vital signs, or the development of a new medical condition. The investigator will be responsible for making medical/safety decisions regarding the participants continuing in the study.
- At the request of the participant for any reason (or none)
- At the request of the sponsor

Document ID:	N/A	Document title:	Classification:	For internal use
		Clinical Study Protocol		
Modified:	24Jun2024		Author:	[name]
Version:	1.0		Approvers:	[name]/[name]
Status:	Final		Page:	17 of 29

- Non-compliance, as defined by failure to respond to phone and/or email contact after three attempts made by a study representative or failure to attend study appointment(s) (lost to follow-up), or being unwilling/unable to consistently use PAP (at least 4 days per week) along with the provided mask
- If the study mask/s provided is/are found to be inadequate for use (e.g., seal, stability, comfort, air flow, etc.)
- If eligibility status changes during the study and the participant no longer meets inclusion or exclusion criteria

The study team will document whether or not each participant completed the study. If, for any participant, study treatment or assessments were discontinued, the reason will be recorded. No further data will be collected following study withdrawal. Each patient's health care provider will be responsible for follow-up care following study withdrawal with communication from research staff.

Participants may withdraw from the study at any time. Withdrawal from the study will not affect their medical treatment or future participation in a research study.

Treatment of Subjects

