Risk and Benefit Analysis

Philips has determined that participation in this study poses minimal risk. It is the opinion of the Sponsor and the PI that the benefits of this protocol outweigh the risks. Both masks being used in the study have been cleared for marketing by the US FDA.

Anticipated Clinical Benefits

Participation in this trial will not result in direct benefit to the participant.

Anticipated Adverse Device Effects

Overall, the risks in this study are minimal and not expected to be different from those encountered by patients prescribed PAP therapy outside of research; however, potential risks are listed below, and they will be described in the ICF and will be repeated verbally to the participants during the consenting process.

Possible risks or effects from use of the products in this research study include, but are not limited to:

- The presence of redness, marks, indentations and/or pressure wherever the mask or headgear touches the face.
- Skin irritation, skin breakdown, bruising or blisters where the mask or headgear comes in contact with the face.
- Discomfort or irritation (itchiness, excessive tearing, burning, dryness, puffiness, infection, blurred vision) of the eyes.
- Eye pain.
- Dry mouth or upper airway.
- Nasal irritation, a feeling of a dry nose, nose bleeds or excessive running of the nose.
- Stomach distension, belching.
- Claustrophobia.
- The study mask may deliver airflow differently from what the participant is accustomed to, and as such, breathing may feel more difficult than what they would experience with a different mask.
- Unusual chest discomfort, breathing discomfort, or shortness of breath.
- Headaches or increased drowsiness.
- In rare cases, the mask may cause tooth, gum, or jaw soreness or aggravate an existing dental condition.
- Pressure or pain in the ears.

Document ID:	N/A	Document title:	Classification:	For internal use
		Clinical Study Protocol		
Modified:	24Jun2024		Author:	[name]
Version:	1.0		Approvers:	[name]/[name]
Status:	Final		Page:	25 of 29

- The participant's condition may not improve or may worsen while participating in this study.

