Careful mask application, sizing, and adjustment should address or correct mask-related issues. Participants should be instructed to avoid overtightening the headgear and to only use the mask when the device is on and blowing air to avoid rebreathing exhaled air and potential suffocation. Note that some rebreathing may occur at low pressures. Breathing discomfort should be transient or can be addressed with counseling. However, all of these complications are normally encountered while using PAP therapies, and there should be no additional risk from participating in this study given that participants will be recruited on the basis of being established on therapy.

If a participant reports they have experienced an adverse event, they will be directed to contact the site study staff and instructed to discontinue therapy if appropriate.

Participation Risk:

- The loss of confidentiality is a potential risk of being in the study, but the site and sponsor will do everything to make sure that participant information is protected.
- Participants may experience frustration, fatigue, and anxiety while completing the study activities.

There may be a possibility of unanticipated or unknown risks; however, for this activity Philips has determined that this risk is low.

Publication and Registration

This study will be registered on ClinicalTrials.gov. There may be plans to publish the results of this trial, beyond the use of the data in marketing materials.

Document ID:	N/A	Document title:	Classification:	For internal use
		Clinical Study Protocol		
Modified:	24Jun2024		Author:	[name]
Version:	1.0		Approvers:	[name]/[name]
Status:	Final		Page:	26 of 29

References

2. Adult Obstructive Sleep Apnea Task Force of the American Academy of Sleep Medicine. Clinical Guideline for the Evaluation, Management and Long-term Care of Obstructive Sleep Apnea in Adults. *Journal of Clinical Sleep Medicine*. 2009;05(03):263-276. doi:10.5664/jcsm.27497

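### Magnets are an exclusion hazard but are missing from the risk list that feeds consent, and no magnet question or request to report a change is planned after Visit 1

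*Combined protocol and SAP*

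**What the plan says.** **Exclusion Criteria.** Two criteria concern magnets. One is "Advised by a health care provider to avoid magnets". The other reaches beyond the participant: "Patient or patient's household member, caregiver or bed partner in close vicinity currently using medical implants or medical devices that would be affected by magnets". It is followed by 20 example implants and devices, among them pacemakers, shunts and infusion pumps.

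**Products Cleared for Marketing by the US FDA.** For the AirFit F40: "Headgear adjustments can be made with magnetic clips that easily snap on and off". The Amara View headgear "attaches to the frame with either magnetic clips or non-magnetic talon clips"; the version to be used in the study is not given.

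**Baseline Visit (Visit 1) and Schedule of Events.** A preliminary eligibility assessment of unspecified content takes place at Pre-Screen. The eligibility questionnaire (Appendix III, self-reported) is marked at Visit 1 only.

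**Visit 2.** The text goes from the survey on the first mask to fitting and then dispensing the second. No eligibility question is listed.

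**Withdrawal.** One ground for discontinuation is "If eligibility status changes during the study and the participant no longer meets inclusion or exclusion criteria".

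**Anticipated Adverse Device Effects.** The section says that "potential risks are listed below, and they will be described in the ICF". The list has no entry on magnets and none on risk to anyone but the participant. After discussing the listed complications, it says that "there should be no additional risk from participating in this study", because participants are already established on therapy.

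**The concern.** A hazard serious enough to keep people out of the study, on account of their own implants or those of people around them, would be expected in the list that tells participants what to watch for. The list is detailed enough to name belching and jaw soreness, but it leaves magnets out.

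The second difficulty is time. The household criterion asks about devices in current use, so it describes the day it is asked. The surgery criterion, by contrast, looks ahead through the trial period, though only for the participant and only for certain body regions. If a bed partner receives an implant after Visit 1, the ground for discontinuation in the Withdrawal section applies on its face, but no scheduled step would bring the change to the site's attention. The person best placed to notice is the participant, and the protocol does not ask the participant to report it.

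At stake is the safety of participants and of people nearby, and complete disclosure. No efficacy estimate depends on this point.

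**Working it through.** There is no trial figure to reproduce. The check sets the sections side by side and then sizes the gap.

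**1. Is the hazard disclosed where the protocol says risks are disclosed?** Magnets appear in the product descriptions and in Exclusion Criteria. They do not appear in Assessment of Safety, whose minimal-risk statement rests on both masks being cleared for marketing, or in Anticipated Adverse Device Effects. The reason given there for expecting no added risk is prior PAP use. That does not cover magnets: current users of either study mask are excluded, and nothing is required of the clip type on the participant's own mask. A participant may therefore meet magnetic clips for the first time in this study.

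**2. What would detect a changed status after Visit 1?**

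| Planned step | Covers the participant | Covers household, caregiver, bed partner |
|---|---|---|
| Eligibility questionnaire, Visit 1 only | Yes, on that day | Yes, on that day |
| AE inquiry at each visit | Partly, if linked to an event | No |
| Look-ahead surgery exclusion | Head, neck, face or lungs only | No |
| Instruction to contact the site | Sizing problems; adverse events | No |
| Instructions for Use with each mask | Content not shown | Content not shown |

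For people other than the participant, no step after Visit 1 is shown to ask the question.

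**3. Age of the check.** Visit 2 is on day 15 ± 5, so the check is 10 to 20 days old when the second mask is dispensed. Visit 3 is on day 30 ± 5, so it is 25 to 35 days old by then.

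**4. Who first receives the AirFit F40 at Visit 2?** The allocation ratio is not stated. Assuming 1:1, 40 / 2 = 20. If only the expected 30 completers are counted, 30 / 2 = 15. For these participants Visit 2 is the first study exposure to magnets only if their Amara View has non-magnetic clips.

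**5. Chance of at least one change before Visit 2.** The documents give no rate, so annual rates r of 1%, 5% and 10% per participant household are assumed, constant and independent. Participant-years T = 20 × days / 365.25; chance = 1 − (1 − r)^T.

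| Days to Visit 2 | T | r = 1% | r = 5% | r = 10% |
|---|---|---|---|---|
| 10 | 0.548 | 0.55% | 2.8% | 5.6% |
| 15 | 0.821 | 0.82% | 4.1% | 8.3% |
| 20 | 1.095 | 1.1% | 5.5% | 10.9% |

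These are chances of any change in the whole group, not of harm.

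**The case against.** The strongest reply is that the protection is already in place. The exclusion applies whatever the mask order, the questionnaire is completed before either mask is handed over, and participants attest to their answers, which include the magnet criteria. All of this stands, and it limits the point. A reader might infer that the exclusion is not enforced for the Amara View-first sequence. That is not so: anyone reporting a contraindication at Visit 1 receives neither mask. What remains is a change after that visit. Changes during home use can arise in either sequence, and a Visit 2 question would not catch those that follow dispensing.

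Three other strong readings also fail:

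- **That participants are not told of the hazard.** The consent form, the survey forms and the Instructions for Use are not in the documents, the risk list is expressly open-ended, and participants meet the magnet questions at Visit 1. Only the protocol's own list can be faulted.
- **That the changed-eligibility ground can never operate.** A participant may volunteer the information at a visit or by telephone, and the investigator has discretion. The accurate statement is that nothing scheduled prompts it.
- **That the no-additional-risk sentence contradicts the exclusions.** In context it concerns the complications just listed, in a population already screened for magnets. It is unreconciled with the exclusions, not contradictory to them.

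It can also be said that the probability is small and the rate undocumented. That is correct. But the gap in the risk list does not depend on the rate: an open-ended list is meant for what was not foreseen, and this hazard was foreseen in detail.

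**Conclusion.** The point holds in a limited form. The protocol screens for magnet-affected devices in participants and those around them, then omits magnets from the list meant to inform consent. It also has a ground for discontinuation on changed eligibility with no scheduled magnet question after Visit 1 and no request to report a change. The disclosure gap is the firmer part, because it rests on the text alone.

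The gap before Visit 2 is small. It concerns about 20 participants under assumed 1:1 order, with about a 0.8% to 8% chance of any change by day 15 at the illustrative rates. Whether Visit 2 is their first study contact with magnets cannot be settled until the Amara View clip type is stated. The case for changing the text rests on consistency, the possible consequence for an implant wearer and the very low cost, not on a high event rate.

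**What to change.** 1. Under Anticipated Adverse Device Effects, and hence in the consent form, add magnetic interference with implants or devices, for the participant and for people in close vicinity. Ask participants to tell the site if this status changes. This also covers changes after Visit 2.
2. At Visit 2, before the second mask is dispensed, repeat the existing magnet items of Appendix III, and mark this in the Schedule of Events. Only the magnet items are needed; this argument does not support repeating the rest of the questionnaire.
3. State which Amara View clip type is supplied, and reconcile the minimal-risk wording in Assessment of Safety and the no-additional-risk sentence with Exclusion Criteria.

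Management of any changed status stays with the investigator under the existing Withdrawal provisions; no new clinical rule is proposed.

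The cost is about two minutes at an existing visit, using questions already written, plus small edits to the protocol and consent form. The downside is an occasional withdrawal under a provision the protocol already contains.

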Participants who complete Visit 3 and return both of their study masks will be compensated \$250.00 for their time and participation in the study. Pro-rated compensation will be provided to participants who voluntarily drop out of the study or are withdrawn from the study by the investigators or their designee (e.g., due to an AE). In that scenario, participants will be reimbursed based on the following schedule:

Visit	Activity	Timing	Payment Amount
Visit 1	Consent/Eligibility/Surveys	~30 minutes	\$50
	Mask Fitting	~30 minutes	\$50
Visit 2	Follow-up Survey	~30 minutes	\$50
Day 15 (± 5 days)	Mask Fitting	~30 minutes	\$50
Visit 3	Follow-up Survey	~30 minutes	\$50
Day 30 (± 5 days)			

Document ID:	N/A	Document title:	Classification:	For internal use
		Clinical Study Protocol		
Modified:	24Jun2024		Author:	[name]
Version:	1.0		Approvers:	[name]/[name]
Status:	Final		Page:	13 of 29

Total paid after Visit 3	\$250
-------------------------------------	--------------

Participants will be asked to return study products at visits 2 and 3. They will not be compensated for study participation until all study products have been returned. Should participants not bring all study products for return at visit 3, they will be compensated at a later date upon return of all study products.

Standard Clinical Care

Each patient's health care provider will be responsible for the ongoing clinical care of each participant. Philips will not make any adjustments or recommendations regarding PAP device settings, beyond troubleshooting aspects of mask fit if necessary.

Stopping Rules

No stopping rules (for the trial) or discontinuation rules (for individual participants) are specified. Participants may choose to withdraw voluntarily or may be withdrawn by investigators on a case-by-case basis (see below).

Schedule of Events

Procedures	Performed/ supervised by	Pre-Screen	Visit 1	Visit 2 Day 15±5 days	Visit 3 Day 30±5 days
Preliminary eligibility assessment	Investigator/ Designee	X			
Consent (enrollment)	Investigator/ Designee		X		
Eligibility questionnaire	Study Coordinator		X		
Demographic & Baseline questionnaires	Study Coordinator		X		
Mask Fitting Survey	Clinician		X	X	
Dispense Study Mask	Clinician/Study Coordinator		X	X	
Mask Survey	Clinician/Study Coordinator			X	X
Inventory check to ensure product return	Clinician/Study Coordinator				X
Compensation	Study Coordinator	X	X	X	X

Document ID:	N/A	Document title:	Classification:	For internal use
		Clinical Study Protocol		

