All AEs must have their relationship to study intervention assessed by the PI or designee who examines and evaluates the subject based on temporal relationship and his/her clinical judgment. The degree of certainty about causality will be classified using the categories below. In a clinical trial, the study product must always be suspect.

- *Not Related:* The event is not known to be an effect of the study product/study activity. There is no temporal relationship between the study product/study activity and the event onset. An alternate etiology has been established. The subject never received the study product/study activity.

Document ID:	N/A	Document title:	Classification:	For internal use
		Clinical Study Protocol		
Modified:	24Jun2024		Author:	[name]
Version:	1.0		Approvers:	[name]/[name]
Status:	Final		Page:	19 of 29

- *Possibly Related:* The event is a lesser known or possible effect of the study product/study activity. There is some evidence to suggest a causal relationship and a reasonable temporal relationship between the study product/study activity and the event onset. However, other factors may have contributed to the event.
- *Causally Related:* The event is a known effect of the study product/study activity (e.g., listed in the protocol). There is a temporal relationship between the study product/study activity and the event onset. The event stops with discontinuation of the study product/study activity (and reoccurs on restarting).

The occurrence of an adverse event (AE) or serious adverse event (SAE) may come to the attention of study personnel during study visits and interviews of a study subject presenting for medical care, or upon review by a study monitor.

All AEs will be captured on the appropriate (e)CRF. Information to be collected includes event description, time of onset, clinician's assessment of severity, relationship to study product (assessed only by those with the training and authority to make a diagnosis), and time of resolution/stabilization of the event. All AEs occurring while on study must be documented appropriately regardless of relationship. All AEs will be followed to adequate resolution.

Changes in the severity of an AE will be documented to allow an assessment of the duration of the event at each level of severity to be performed. AEs characterized as intermittent require documentation of onset and duration of each episode.

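### The withdrawal rule bars all later data with no safety exception, so the outcome of an adverse event open at withdrawal may go unrecorded although the safety section requires it

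*Combined protocol and SAP*

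**What the plan says.** All references are to the combined protocol and SAP, version 1.0.

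- **Adverse Event Classification and Reporting**: "All AEs will be followed to adequate resolution". The items to be captured for each AE include "time of resolution/stabilization of the event". Changes in severity are documented so that duration at each severity level can be assessed. For SAEs and UADEs only, the section asks the site to send the sponsor a new report as more information arrives.
- **Withdrawal**: "No further data will be collected following study withdrawal". The same section gives AEs as a reason for the investigator to discontinue a participant: "Such a decision may be precipitated by adverse events, including fever, nausea, rash". It makes the participant's own provider responsible for "follow-up care following study withdrawal with communication from research staff".
- **Participant Reimbursement**: an AE is the example given of why an investigator might withdraw someone.
- **Safety Analysis**: AE follow-up stops at resolution or at completion of the study, whichever is earlier. AEs are listed and not compared statistically.
- **Number of Subjects**: about 40 enrolled, about 30 expected to complete.

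**The concern.** The two main rules point in opposite directions for an AE that has not resolved when the participant leaves. One requires an end date; the other forbids collecting anything more and makes no exception for safety data. The case is foreseeable, because the plan itself names AEs as a trigger for withdrawal. The anticipated effects listed under Anticipated Adverse Device Effects include skin breakdown, blisters and eye infection, which need not have cleared on the day of exit.

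What is at stake is the completeness of the AE listing. Occurrence, onset, severity, relationship and the reason for withdrawal are still recorded. The outcome and its date may be missing, and for the participants in whom they are most informative: those who left with an event still open, possibly because of it.

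**Working it through.** The check is a comparison of rules; the plan states no figure on this point to reproduce.

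**1. Apply the rules to each situation.**

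| Situation | AE reporting section | Withdrawal section | Safety Analysis section | Result |
|---|---|---|---|---|
| AE resolved before exit | End date recorded | Not engaged | Satisfied | No conflict |
| Non-serious AE open at withdrawal | Follow to resolution; record end date | No further data | Does not address withdrawal | Both main rules cannot be followed literally |
| Serious AE open at withdrawal | As above, plus updated reports to the sponsor | No further data; no exemption for serious events | Does not address withdrawal | Same literal conflict, but a specific update route exists |
| AE open when a completer reaches Visit 3 | Follow to resolution | Not engaged | Stops at study completion | Depends on what that term means |

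**2. Look for text that removes the conflict at withdrawal.** The provider arrangement keeps care going and mentions communication from research staff. It does not say that an AE outcome may be entered in the CRF. The AE recording window, from consent to the last day of participation, limits start dates and not follow-up, so it neither causes nor cures the conflict.

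**3. Read the Safety Analysis cutoff.** The term *study completion* is not defined. Data Handling and Recordkeeping uses it for record retention, apparently meaning the end of the trial. On that reading only AEs open when the trial ends are cut off. The Withdrawal section speaks of "whether or not each participant completed the study", and Conclusion of Participation says when an individual's participation ends. On that reading an AE open at Visit 3 is cut off as well. On either reading the cutoff can fall before the resolution that the AE reporting section requires.

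**4. Scale.** Inputs from Number of Subjects: about 40 enrolled, about 30 completing.

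- Expected non-completers: 40 − 30 = 10.
- Share: 10 / 40 = 25%.
- Consistency: 30 / (1 − 0.25) = 40.

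The 25% is implied by the two counts; the plan states no dropout rate. The 10 leave for any reason, including loss to contact, and the documents give no AE rate. The number who would leave with an open AE therefore cannot be derived.

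**The case against.** The best reply is that the withdrawal sentence was meant for study assessments. It follows directly on a sentence about discontinued treatment or assessments, and the next sentence keeps research staff in touch with the provider. The AE section's references to adequate resolution and to stabilization leave room for judgement. On this view the specific safety rule prevails over the general sentence and no outcome is lost. That reading is possible, but it is not what the sentence says, and a site or monitor applying it as written would stop collecting. The consent form and the AE CRF were not available to this review. Either might already allow outcome contact after withdrawal or an entry of *ongoing*.

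Several other counter-arguments stand and limit the point:

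- **Serious events.** A reader might infer that only non-serious AEs are exposed, because serious ones have an update route. The withdrawal sentence exempts neither kind. The route makes loss less likely for serious events but does not remove the literal bar.
- **The cutoff in Safety Analysis.** A reader might treat it as a defect of equal weight. Ending AE follow-up when a study ends is ordinary practice; only its wording disagrees with the AE reporting section.
- **The 60-day limit.** A reader might infer that Conclusion of Participation forbids later calls. It limits time active in the study and does not bar a call to learn an outcome.
- **Duration by severity.** A missing end date leaves only the final severity level open; earlier levels are bounded by the recorded changes.
- **Causality.** A reader might infer that relationship can no longer be assigned. It is judged on timing and clinical judgement, which is possible at withdrawal, although information on whether the event stopped afterwards would be absent.

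**Conclusion.** The point holds as a conflict between two current rules. For an AE open at withdrawal, literal compliance with the Withdrawal section leaves its outcome and end date out of the listing, contrary to the AE reporting section. The Safety Analysis cutoff needs alignment only.

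The effect is modest. The number of affected events is unknown. The 10 of 40 expected non-completers is context for scale: it should not be read as a ceiling, since both counts are approximate expectations, nor as an estimate of open AEs.

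A reader might also infer that withdrawn participants are left without care or that the trial's comparisons are affected. The documents support neither: care stays with the provider, AEs are listed without statistical comparison, and no preference or device endpoint changes.

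The conclusion assumes that sites apply the withdrawal sentence as written and that neither the consent form nor the CRF already provides for outcome follow-up. It is a low-cost change worth considering, held with medium confidence.

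**What to change.** 1. **Withdrawal section.** Keep "No further data will be collected following study withdrawal" and add an exception: the outcome, and the date of resolution or stabilization, of AEs with onset before withdrawal, where the participant agrees.
2. **Adverse Event Classification and Reporting, and Safety Analysis.** State the same end point in both: follow each AE to resolution or stabilization, or otherwise to last contact or database lock. Events still open then are listed as ongoing, with the date. Both sections need the edit; leaving the AE reporting section as it stands while adding cutoffs elsewhere would keep a mismatch.

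Participants already lost under the existing rule ("failure to respond to phone and/or email contact after three attempts") need no further calls; their open AEs are listed as ongoing at last contact. Conclusion of Participation needs no change.

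The cost is a few telephone calls, possibly one line in the consent form if it does not already allow such contact, and IRB review of the amended wording. Visits, sample size and endpoints are unchanged.
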